#### 6.3 Outcome variables and study follow-up:

6.3.1 Outcome variables

Safety outcome variables of interest (definitions provided in **Appendix**):

- Primary outcome: Major bleeding and clinically relevant non-major bleeding through 365 days of treatment with apixaban or rivaroxaban.
- Secondary outcomes:
  - To assess the frequency of major bleeding events and clinically relevant non-major bleeding individually
  - $\circ$   $\,$  To assess the frequency of intracranial and extracranial bleeding events
  - o Stroke
  - $\circ$  All-cause mortality

6.3.2 Study follow-up

Both as-treated (AT) and intention-to-treat (ITT) analyses will be conducted with treatment defined as the index drug on day of cohort entry. The **as-treated** will be the primary analysis. An allowable gap of 10 days between records indicating each treatment will qualify as "continuous therapy" with respect to follow-up in the as-treated analysis.

The follow-up will start the day after drug initiation (i.e., cohort entry date), and will continue until the earliest date of the following events:

- The first occurrence of the outcome of interest
- The date of end of continuous registration in the database
- End of the study period at 365 days
- Measured death event occurs
- Switch
- Discontinuation (10-day allowable grace period and risk window)
- Nursing home admission
- Initiation of another anticoagulant (dabigatran, heparin, warfarin, etc.)

In the secondary ITT analysis, we will not censor for discontinuation, switching among study drugs, or addition of other anticoagulants

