#### 5. Cohort Identification

#### 5.1 Cohort Summary

An active-comparator, new-user design, propensity score matched, cohort study will be applied to compare patients that received apixaban vs. rivaroxaban. Patients will enter the cohort upon initiation of apixaban or rivaroxaban after a 180 day washout without anticoagulant exposure. They will be required to have a diagnosis code indicating non-valvular atrial fibrillation in the prior 180 days, and be age 18 or older on the date of initiation of therapy. Subjects will be excluded if they have had any indication of stage IV or V CKD, ESRD, an active bleeding episode, cancer, obesity, liver disease, or another indication for long-term anticoagulation, such as hospitalization for DVT or PE, in the prior 180 days. Patients will also be excluded if they have used any contraindicated medications in the prior 180 days or had an indication for atrial fibrillation that was not non-valvular. All patients were required to have continuous enrollment for 180 days prior to cohort entry to ensure incident use of the study drugs.

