Exclusion of Pregnancy [-180,0]	-3 (<1%)	112,908	-4 (<1%)	91,980		
Exclusion of Coagulopathy [-180,0]	-958 (<1%)	111,950	-320 (<1%)	91,660		
Final cohort		111,950		91,660		325,926

 $^{\ast}\text{CMS}$  cell suppression policies may result in omitted data

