#### 6.2 Preliminary Covariates:

- Age
- Gender
- CCI score

The covariate listed above represents only a small subset of the covariate vector that will ultimately be controlled for in the design and analysis. We use the covariates above only for initial feasibility analyses to judge whether there is likely to be sufficient overlap between treatment groups to proceed with the study. Remaining covariates are defined only after the study has passed the initial feasibility analysis and the initial power assessment and are listed in Table 1 (**Appendix B**).

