#### For Apixaban vs Rivaroxaban

CENSORING REASONS FOR STUDY OUTCOME								
Reasons	Optum CDM	IBM® MarketScan®	CMS - NOAC					
Outcome	2,226 (2.0%)	2,570 (2.8%)	17,135 (5.3%)					
Death	852 (0.8%)	38 (0.0%)	3,744 (1.2%)					
Start of an additional exposure	1,423 (1.3%)	1,250 (1.4%)	5,584 (1.7%)					
End of index exposure	71,747 (64.2%)	55,668 (60.9%)	189,840 (58.3%)					
Maximum follow-up time reached	16,894 (15.1%)	12,797 (14.0%)	42,722 (13.1%)					
End of patient data	18 (0.0%)	5,277 (5.8%)	38,454 (11.8%)					
End of patient enrollment	5,827 (5.2%)	11,391 (12.5%)	4,681 (1.4%)					
Other Anticoagulant Use + Nursing Home Admission	12,848 (11.5%)	2,444 (2.7%)	23,319 (7.2%)					

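### Nursing home admission ends follow-up, but nursing-home residence at entry is neither an exclusion nor a propensity-score covariate

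*Combined protocol and SAP*

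**What the plan says.** Section 6.3.2 starts follow-up on the day after drug initiation and ends it at the earliest of several events, one of which is "Nursing home admission". It gives no code list, claim type, minimum stay or requirement that the admission be new. The sentence on the second analysis reads: "In the secondary ITT analysis, we will not censor for discontinuation, switching among study drugs, or addition of other anticoagulants". Nursing home admission is not among those exemptions.

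On entry, section 5.1 excludes patients with "stage IV or V CKD, ESRD, an active bleeding episode, cancer, obesity, liver disease" and some further conditions, indications and medications, none of which concerns a care facility. The section 5.3 flowchart ends with pregnancy and coagulopathy and has no facility step. The readable criteria in Appendix A have none either. Section 9 puts every listed covariate into the propensity score, and the Appendix B tables list no nursing-home, skilled-nursing or long-term-care variable.

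In the section 7 censoring table the event appears only in a combined row, "Other Anticoagulant Use + Nursing Home Admission".

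**The concern.** A censoring event that can already be present at baseline needs a baseline counterpart. Otherwise an existing state may be recorded as something that happened after entry. Here a resident who fills either drug can enter the cohort and be matched. If any facility claim counts as an admission, that patient may leave follow-up early for a reason that predates treatment. If only new admissions count, the patient stays in follow-up, and residence is a prognostic factor that the propensity score does not contain. The plan does not say which applies.

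At stake are a clear target population, the possibility of selective early censoring, and any residual confounding by residence that the measured frailty variables leave behind. As written, the ITT analysis gives no check, because it keeps the same censoring rule.

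**Working it through.** **1. Is there a hidden baseline exclusion?** Subtracting each flowchart exclusion from the preceding count gives the next printed count at all 21 steps in Optum and all 21 in MarketScan. In CMS the printed steps close to within one patient (708,232 − 264,650 = 443,582; printed 443,581). The last printed CMS count before the final cohort leaves 327,709 − 325,926 = 1,783 patients (0.54%). These fall on the pregnancy and coagulopathy rows, which are blank for CMS. The same two rows remove 961/112,911 = 0.85% in Optum and 324/91,984 = 0.35% in MarketScan, so the CMS remainder is of the expected size. No nursing-home step is listed in any database.

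**2. What does the propensity score hold instead?** Appendix B, matched, pooled, rivaroxaban vs apixaban:
- frailty score: mean 0.18 vs 0.18
- dementia: 6.9% vs 6.9%
- delirium: 2.4% vs 2.3%
- falls: 2.9% vs 2.9%
- hospitalizations: mean 0.34 vs 0.33
- hospital days: mean 1.76 vs 1.75

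Frailty is therefore adjusted for through several proxies, all closely balanced. Residence is not among them.

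**3. How large is the reported censoring reason?** The section 7 rows sum to 111,835 (Optum), 91,435 (MarketScan) and 325,479 (CMS), 528,749 in total.
- Merged reason: 12,848 + 2,444 + 23,319 = 38,611.
- Share: 38,611/528,749 = 7.3%.
- Primary events, for scale: 2,226 + 2,570 + 17,135 = 21,931.

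This is a ceiling on nursing-home censoring in that table. It is not a count of residents at entry.

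**4. Does the merged reason differ by arm?** The section 9 table (dummy outcome) gives 9,772 for rivaroxaban and 12,458 for apixaban. Over the unmatched pooled arms in Appendix B:
- 9,772/230,439 = 4.24%
- 12,458/298,310 = 4.18%

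**5. Would a baseline exclusion cost power?** With d events, 1:1 allocation and two-sided alpha 0.05, power = Φ(|ln HR| × √(d/4) − 1.96). For Optum in section 10, d = 68,134 × 19.8838767/1,000 = 1,354.77. At HR 0.8, 0.2231 × √338.69 − 1.96 = 2.147, and Φ(2.147) = 0.984. This reproduces the stated 0.98409053, the lowest power in the final tables.

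The share resident at entry is not given. Assume it is 1% to 10% of the matched set, with events falling in proportion:

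| Assumed loss | Optum | MarketScan |
|---|---|---|
| 1% | 0.983 | 0.996 |
| 3% | 0.981 | 0.996 |
| 5% | 0.980 | 0.995 |
| 10% | 0.974 | 0.993 |

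CMS and pooled power stay at 1.0 throughout.

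**The case against.** The strongest reply is that the mechanism is conjectural. If an admission means a new one, a patient already resident is not censored at the next facility claim. This stands: early censoring of residents is possible under the text, not established by it.

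A second reply is that the two harms limit each other. Residents who are censored almost at once contribute little person-time and few events, so they can hardly confound the hazard ratio. Residents who remain in follow-up are not being selectively removed. This also stands, and it means the two harms cannot both apply at full strength.

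Third, the matched analysis already balances frailty, dementia, delirium, falls and hospital use. What remains is residual confounding by residence given all of these.

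Fourth, a reader might infer that residence differs by arm, because apixaban users are older before matching. The only by-arm data do not support that: the merged reason is 4.2% in each arm. They do not exclude it either. The table uses the dummy outcome, combines two reasons whose differences could cancel, and describes a different follow-up pattern: 62.1% reach maximum follow-up there, against 13.1% to 15.1% in the section 7 table.

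Finally, the readable trial exclusions in Appendix A contain no nursing-home criterion, so removing every patient with any recent facility claim would move away from the trial being emulated and could drop people who had a short stay and went home. That favors a covariate for earlier stays, with exclusion kept for stays that cover day 0.

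**Conclusion.** The asymmetry is real and can be read directly from the plan: an undefined nursing-home event ends follow-up in the as-treated analysis and, as written, in ITT, with no baseline exclusion or covariate to match it. What is at issue is selective early censoring or residual confounding beyond the balanced proxies. The size cannot be stated, because the number resident at entry is not given.

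Three stronger readings are tempting and unsupported. That the frailest patients are enrolled and then promptly censored depends on an admission algorithm the plan does not give. That the 38,611 censored patients measure the problem is wrong, because the figure merges two reasons and counts censoring after entry. That the spread of the merged row across databases (11.5% Optum, 2.7% MarketScan, 7.2% CMS) shows an inconsistent nursing-home measure does not follow, because the spread cannot be assigned to either component.

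This is an inexpensive design improvement. No bias has been demonstrated.

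**What to change.** Define the nursing-home algorithm and apply that same algorithm at baseline. Add any stay in [-180, -1] to the propensity score, exclude patients whose stay covers day 0 so that the follow-up event is a new admission, add that exclusion to the flowchart, and re-match. State in section 6.3.2 whether the rule applies in ITT. Report nursing home admission separately from other anticoagulant use, by arm and database. The last item affects reporting only.

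The cost is one exclusion, one covariate and a re-match, with a slightly smaller cohort and a small departure from the trial's entry criteria. Section 13 shows no comparative analysis as conducted, so the change can still be prespecified.

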#### 7. Initial Feasibility Analysis

#### Aetion report name:

For apixaban vs. rivaroxaban Optum CDM - https://bwh-dope.aetion.com/projects/details/1813/rwrs/78411 IBM® MarketScan®- https://bwh-dope.aetion.com/projects/details/1814/rwrs/78632 CMS NOAC - https://bwh-dope.aetion.com/projects/details/1814/rwrs/78632

Date conducted: 01/28/2022

Complete Action feasibility analysis using age, gender, and CCI as the only covariates and the primary endpoint (Section 6.3.1) as the outcome. No measures of association will be computed, nor will incidence rates be stratified by treatment group.

• Report patient characteristics by treatment group

### Apixaban vs Rivaroxaban

		Optum CDM			IBM® MarketScan® CMS - NOAC				
Variable	Rivaroxaban - Comparator	Apixaban - Exposure	Difference	Rivaroxaban - Comparator	Apixaban - Exposure	Difference	Rivaroxaban - Comparator	Apixaban - Exposure	Difference
Number of patients	39,628	72,322		41,932	49,503		148,933	176,546	
Age									
mean (sd)	71.62 (10.97)	74.33 (10.15)	-2.71 (-2.84, -2.58)	66.38 (12.81)	68.13 (13.18)	-1.75 (-1.92, -1.58)	76.19 (8.31)	77.68 (8.32)	-1.49 (-1.55, -1.44)
median [IQR]	73.00 [66.00, 80.00]	75.00 [68.00, 82.00]		65.00 [58.00, 76.00]	67.00 [59.00, 79.00]		76.00 [70.00, 82.00]	77.00 [72.00, 84.00]	
Gender									
М	22,048 (55.6%)	35,362 (48.9%)	6.7% (6.1%, 7.4%)	25,981 (62.0%)	28,450 (57.5%)	4.5% (3.8%, 5.1%)	69,102 (46.4%)	74,655 (42.3%)	4.1% (3.8%, 4.5%)
F	17,580 (44.4%)	36,960 (51.1%)	-6.7% (- 7.4%, -6.1%)	15,951 (38.0%)	21,053 (42.5%)	-4.5% (- 5.1%, -3.8%)	79,831 (53.6%)	101,891 (57.7%)	-4.1% (- 4.5%, -3.8%)
U									
CCI (180 Days									
mean (sd)	2.18 (2.11)	2.63 (2.37)	-0.45 (-0.48, -0.42)	1.53 (1.58)	1.80 (1.80)	-0.27 (-0.29, -0.24)	1.83 (1.81)	2.04 (1.95)	-0.21 (-0.22, -0.20)
median [IQR]	2.00 [1.00, 3.00]	2.00 [1.00, 4.00]		1.00 [0.00, 2.00]	1.00 [0.00, 3.00]		1.00 [0.00, 3.00]	2.00 [1.00, 3.00]	

#### • Report summary parameters of study population **FEASIBILITY- FOR STUDY OUTCOME**

For Apixaban vs Rivaroxaban

FEASIBILITY FOR STUDY OUTCOME								
	Optum CDM	IBM® MarketScan®	CMS - NOAC					
Number of patients in full cohort	111,950	91,660	325,926					
Number of patients dropped as incomplete cases	0	0	0					
Number of patients that did not begin follow-up	115	225	447					
Number of patients in analytic cohort	111,835	91,435	325,489					
Number of events	2,226	2,570	17,135					
Number of person-years	44,062.25	35,513.75	126,012.26					
Number of patients in group: Rivaroxaban - Comparator	39,574	41,932	148,933					
Number of patients in group: Apixaban - Exposure	72,261	49,503	176,546					
Risk per 1,000 patients	19.9	28.11	52.65					
Rate per 1,000 person-years	50.52	72.37	135.98					

- Report median follow-up time by treatment group
  - For Apixaban vs Rivaroxaban

FOLLOW-UP TIME FOR STUDY OUTCOME Median Follow-Up Time (Days) [IQR] – At 10 days gap								
Patient Group Optum CDM IBM® MarketScan® CMS - No								
Overall Patient Population	98 [38, 235]	98 [38, 222]	98 [38, 222]					
Referent - Rivaroxaban	98 [38, 222]	98 [38, 219]	98 [38, 219]					
Exposure - Apixaban	98 [38, 243]	98 [38, 225]	98 [38, 226]					

• Report reasons for censoring in the overall study population

#### For Apixaban vs Rivaroxaban

CENSORING REASONS FOR STUDY OUTCOME								
Reasons	Optum CDM	IBM® MarketScan®	CMS - NOAC					
Outcome	2,226 (2.0%)	2,570 (2.8%)	17,135 (5.3%)					
Death	852 (0.8%)	38 (0.0%)	3,744 (1.2%)					
Start of an additional exposure	1,423 (1.3%)	1,250 (1.4%)	5,584 (1.7%)					
End of index exposure	71,747 (64.2%)	55,668 (60.9%)	189,840 (58.3%)					
Maximum follow-up time reached	16,894 (15.1%)	12,797 (14.0%)	42,722 (13.1%)					
End of patient data	18 (0.0%)	5,277 (5.8%)	38,454 (11.8%)					
End of patient enrollment	5,827 (5.2%)	11,391 (12.5%)	4,681 (1.4%)					
Other Anticoagulant Use + Nursing Home Admission	12,848 (11.5%)	2,444 (2.7%)	23,319 (7.2%)					

#### • Report overall risk of the primary outcome.

	Optum CDM	IBM® MarketScan®	CMS - NOAC	Pooled
Risk per 1,000 patients	20.2089659	27.7425893	53.4783969	41.4990646

#### 8. Initial Power Assessment

#### Aetion report name:

- For Apixaban vs Rivaroxaban
  - Optum CDM https://bwh-dope.aetion.com/projects/details/1813/rwrs/78412
  - IBM® MarketScan®- https://bwh-dope.aetion.com/projects/details/1814/rwrs/78633
  - CMS NOAC https://bwh-dope.aetion.com/projects/details/1831/rwrs/78415

#### Date conducted: 01/21/2022 and 01/28/2022

In order to complete the initial power analysis, a dummy outcome indicating a 90-day gap in database enrollment will be used. This

outcome is used to ensure that no information on the comparative risks of the outcomes of interest are available at this stage. A 1:1 PS-matched comparative analysis was performed, including age, gender, and CCI score as the only covariates. Power calculations are based on the formulas from Chow et al. (2008).

• Stop analyses until feasibility and power are reviewed by primary investigators and FDA. Reviewers evaluate the results of the analyses described above in Sections 7 and 8, including numbers of patients, patient characteristics, follow-up time, and reasons for censoring by treatment group, as well as overall rates of outcomes and study power. These parameters are re-evaluated and reported in the subsequent sections, after incorporating feedback and refining the protocol.

This emulation is of a trial that is not yet completed. The trial investigators have not published their power calculations. Therefore, we present a range of power calculations for different effect sizes given the feasibility counts and an alpha of 0.05. The range in potential hazard rations comes from a meta- analysis of safety and efficacy studies of apixaban in patients with atrial fibrillation (Proietti et al. 2017). The target enrollment for the trial is 3,028 participants. We anticipate a pooled analytic cohort of 529,536 subjects.

1. Pooled

Superiority Analysis - Pooled					
Number of patients matched	454,312	454,312	454,312	454,312	454,312
Reference	227,156	227,156	227,156	227,156	227,156
Exposure	227,156	227,156	227,156	227,156	227,156
Risk per 1,000 patients	41.4155034	41.4155034	41.4155034	41.4155034	41.4155034
Alpha (2-sided	0.05	0.05	0.05	0.05	0.05
Desired HR from RCT	0.8	0.7	0.6	0.5	0.4
Number of events expected	18815.5602	18815.5602	18815.5602	18815.5602	18815.5602
Power	1	1	1	1	1

2. Optum CDM

Superiority Analysis - Optum					
Number of patients matched	78,962	78,962	78,962	78,962	78,962
Reference	39,481	39,481	39,481	39,481	39,481
Exposure	39,481	39,481	39,481	39,481	39,481
Risk per 1,000 patients	19.8838767	19.8838767	19.8838767	19.8838767	19.8838767
Alpha (2-sided	0.05	0.05	0.05	0.05	0.05
Desired HR from RCT	0.8	0.7	0.6	0.5	0.4
Number of events expected	1570.07067	1570.07067	1570.07067	1570.07067	1570.07067
Power	0.99307189	0.99999984	1	1	1

#### 3. IBM® MarketScan®

Superiority Analysis - MarketScan					
Number of patients matched	82,730	82,730	82,730	82,730	82,730
Reference	41,365	41,365	41,365	41,365	41,365
Exposure	41,365	41,365	41,365	41,365	41,365
Risk per 1,000 patients	28.0384028	28.0384028	28.0384028	28.0384028	28.0384028
Alpha (2-sided	0.05	0.05	0.05	0.05	0.05
Desired HR from RCT	0.8	0.7	0.6	0.5	0.4
Number of events expected	2319.61706	2319.61706	2319.61706	2319.61706	2319.61706
Power	0.99967945	1	1	1	1

#### 4. CMS – NOAC

Superiority Analysis – CMS NOAC					
Number of patients matched	292,620	292,620	292,620	292,620	292,620

Effectiveness research with Real World Data to support FDA's regulatory decision making

Reference	146,310	146,310	146,310	146,310	146,310
Exposure	146,310	146,310	146,310	146,310	146,310
Risk per 1,000 patients	52.5732835	52.5732835	52.5732835	52.5732835	52.5732835
Alpha (2-sided	0.05	0.05	0.05	0.05	0.05
Desired HR from RCT	0.8	0.7	0.6	0.5	0.4
Number of events expected	23075.9913	15383.9942	15383.9942	15383.9942	15383.9942
Power	1	1	1	1	1

**5.** Stop analyses until feasibility and power are reviewed by primary investigators, FDA, and assigned members of advisory board.

Reviewed by PI:	Date reviewed:	
Reviewed by FDA:	Date reviewed:	
Reasons for stopping		
analysis (if required):		

#### 9. Balance Assessment

#### Aetion report name:

- Rivaroxaban versus Apixaban
  - o Optum https://bwh-dope.aetion.com/projects/details/1813/rwrs/79770
  - o MarketScan https://bwh-dope.aetion.com/projects/details/1814/rwrs/79771
  - o CMS NOAC https://bwh-dope.aetion.com/projects/details/1831/rwrs/79772

#### Date conducted: 02/25/2022

After review of initial feasibility and power analyses, complete creation of the remaining covariates from Section 6.2. Again, using the

dummy outcome of a 90-day gap in database enrollment, complete a 1:1 PS-matched analysis. The PS should include the complete list of covariates.

6. Provide plot of PS distributions stratified by treatment group.

#### a. See Appendix B

- 7. Report covariate balance after matching.
  - a. See Appendix B
    - i. CMS cell suppression policy may result in omitted data

#### 8. Report reasons for censoring by treatment group.

Censoring Reasons for Study Outcome					
Reasons	Overall	Referent	Exposure		
Death	0 (0.0%)	0 (0.0%)	0 (0.0%)		
Start of an additional exposure	5,906 (1.1%)	2,416 (1.0%)	3,490 (1.2%)		
End of index exposure	8,557 (1.6%)	4,649 (2.0%)	3,908 (1.3%)		
Maximum follow-up time	328,427 (62.1%)	147,012 (63.8%)	181,415 (60.8%)		
End of patient data	74,371 (14.1%)	31,658 (13.7%)	42,713 (14.3%)		
End of patient enrollment	44,450 (8.4%)	16,025 (7.0%)	28,425 (9.5%)		
Other Anticoagulant Therapy + Nursing Home Admission	22,230 (4.2%)	9,772 (4.2%)	12,458 (4.2%)		

#### 9. Report follow-up time by treatment group.

FOLLOW-UP TIME FOR STUDY OUTCOME Median Follow-Up Time (Days) [IQR] – At 10 days gap						
Patient Group	Optum CDM	IBM® MarketScan®	CMS - NOAC			
Overall Patient Population	98 [38, 238]	98 [38, 227]	98 [38, 228]			
Referent - Rivaroxaban	98 [38, 225]	98 [38, 224]	98 [38, 225]			
Exposure - Apixaban	98 [38, 245]	98 [38, 231]	98 [38, 231]			

#### **10. Final Power Assessment**

#### Date conducted: 02/09/2022

- 10. Re-calculate power in the appropriate excel table, using the revised number of matched patients from the PS-match in Section 9. All other parameters in the table should be the same as in Section 8.
- 1. Pooled

Superiority Analysis - Pooled					
Number of patients matched	368,214	368,214	368,214	368,214	368,214
Reference	184,107	184,107	184,107	184,107	184,107
Exposure	184,107	184,107	184,107	184,107	184,107
Risk per 1,000 patients	41.4155034	41.4155034	41.4155034	41.4155034	41.4155034
Alpha (2-sided)	0.05	0.05	0.05	0.05	0.05
Desired HR from RCT	0.8	0.7	0.6	0.5	0.4
Number of events expected	15249.7682	15249.7682	15249.7682	15249.7682	15249.7682
Power	1	1	1	1	1

#### 2. Optum CDM

Superiority Analysis - Optum					
Number of patients matched	68,134	68,134	68,134	68,134	68,134
Reference	34,067	34,067	34,067	34,067	34,067
Exposure	34,067	34,067	34,067	34,067	34,067
Risk per 1,000 patients	19.8838767	19.8838767	19.8838767	19.8838767	19.8838767
Alpha (2-sided)	0.05	0.05	0.05	0.05	0.05
Desired HR from RCT	0.8	0.7	0.6	0.5	0.4

Number of events expected	1354.76806	1354.76806	1354.76806	1354.76806	1354.76806
Power	0.98409053	0.99999793	1	1	1

#### 3. IBM® MarketScan®

Superiority Analysis - MarketScan					
Number of patients matched	61,846	61,846	61,846	61,846	61,846
Reference	30,923	30,923	30,923	30,923	30,923
Exposure	30,923	30,923	30,923	30,923	30,923
Risk per 1,000 patients	28.0384028	28.0384028	28.0384028	28.0384028	28.0384028
Alpha (2-sided)	0.05	0.05	0.05	0.05	0.05
Desired HR from RCT	0.8	0.7	0.6	0.5	0.4
Number of events expected	1734.06306	1734.06306	1734.06306	1734.06306	1734.06306
Power	0.99638561	0.99999998	1	1	1

